## **2.3. Name and description of the device under investigation.**

The Arabin cervical pessary, which is CE-certified for preventing SPB (CE 0482 / EN ISO 13485: 2003 annex III of the council directive 93/42 EEC).  
See annex I.

## **2.4. Statement that testing will be performed according to protocol, GCP and applicable legal requirements.**

The Clinical Trial will be conducted following the protocol, the GCP, and all legal requirements.

## **3. Objective**

This study aims to investigate the benefit of a prophylactic cervical pessary treatment in women at high risk of PTB due to a history of at least one previous preterm delivery before 34+0 weeks and/or a history of late abortion.

## **4. Design**

## 4.1. Specific description of primary and secondary variables.

### 4.1.1. Primary outcome:

- Child's birth and survival

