### 4.1.2. Secondary outcomes:

[figure not shown]
- Offspring
  - Time to birth
    - Preterm birth before 37 weeks: rate of delivery before 36+6 weeks
    - Preterm birth before 34 weeks: rate of delivery before 33+6 weeks
    - Preterm birth before 32 weeks: rate of delivery before 31+6 weeks
    - Preterm birth before 30 weeks: rate of delivery before 29+6 weeks—
    - Preterm birth before 28 weeks: rate of delivery before 27+6 weeks—
  - Birth weight: median weight (g) of the newborns at birth
  - Fetal or neonatal death: rate of intrauterine demise or neonatal death during the first 24 hours
  - Neonatal morbidity: rate of major adverse neonatal outcomes before discharge from the hospital
    - Intraventricular Haemorrhage (IVH): grades III-IV
    - Retinopathy of prematurity
    - Respiratory Distress Syndrome (RDS): grades II-IV,
    - Need for ventilation > 72 h
    - Necrotising enterocolitis
    - Proven or suspected sepsis, antibiotics (>5 days)
    - Need (Duration in days) for neonatal special care (NICU)
  - Harm from intervention
- Mother:
  - Maternal death
  - Significant maternal adverse events (rate):
    - Heavy bleeding: bleeding that requires a medical intervention
    - Cervical tear: cervical rupture due to the pessary placement
    - Uterine rupture: rupture of the uterus due to contractions or surgery
  - Physical or psychological intolerance to pessary: discomfort or pain due to the pessary that makes daily life uncomfortable (number of cases)
  - Rupture of membranes before 32 weeks: rate of—rupture of amniotic membranes before 31+6 weeks
  - Infection/inflammation
  - Hospitalisation for threatened preterm labour before 32 weeks: requirement of hospitalisation due to preterm contractions that need medical treatment to try to stop them before 31+6 weeks (rate)

- Mean hospital stay duration: number of days of admittance at the hospital
- Use of tocolytic treatment: Type of tocolytic, days of treatment, dose

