#### 4.2. Description of the trial design.

Open Multicentre Randomized Controlled Trial, in parallel groups, based on treatment with progesterone comparing the placement of a prophylactic cervical pessary with usual management in singleton pregnancies at high-risk of PTB due to a history of at least one previous preterm delivery and/or a history of late abortion.

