## **6. Efficacy assessment**

### **6.1. Specification of efficacy parameters: Primary and secondary endpoints.**

This study aims to investigate the benefit of a prophylactic cervical pessary treatment in women at high risk of PTB due to a history of at least one previous preterm delivery and/or a history of late abortion on the perinatal outcome .

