## **7. Statistics**

### **7.1. Description of statistical methods.**

A descriptive analysis by preterm birth will be carried out calculating means and medians for quantitative variables and proportions for categorical variables.

Two-sided Z-tests will be used for comparing among exposure and outcomes groups per pregnancy. A multivariate logistic regression will be fitted to control for possible confounders. Relative risks and 95% confidence interval will be calculated for the outcomes.

All analysis will be carried out with SPSS® 19.0 statistical package (IBM Company SPSS Inc. Headquarters, Chicago, Illinois. USA). Statistical significance will be accepted in all cases with a  $p < 0.05$ .

Outcome	Statistical Test
Birth before 34 Weeks of Gestation	Two-sided Z-Test (RR, 95% CI)
Time to Birth	Log-rank test (HR, 95% CI)
Birthweight	Multilevel model (mean $\pm$ SD)
Fetal / Neonatal Death	Two-sided Z-Test (RR, 95% CI)
Neonatal Morbidity	Two-sided Z-Test (RR, 95% CI)
Need for Hospitalization	Two-sided Z-Test (RR, 95% CI)
Days of Hospitalization	Two-sided Z-Test (RR, 95% CI)
Maternal Adverse Events	Two-sided Z-Test (RR, 95% CI)
Pessary Intolerance	Two-sided Z-Test (RR, 95% CI)
Vaginal Infections	Two-sided Z-Test (RR, 95% CI)

the complete data set for the secondary endpoints will be available after the last women enrolled in this study has given birth, so the analysis of these outcome parameter will be done right after this event.

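### The primary outcome in 4.1.1 is too undefined to analyse, and the 80% power in 7.2 is claimed for an outcome that is never named

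*Protocol*

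**What the plan says.** Four places in the protocol should identify the primary outcome.

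- **Section 4.1.1** has one entry, the child's "birth and survival". It gives no success criterion, no time at which survival is judged, and no statement of how a fetal loss counts.
- **Section 6.1** is headed "Specification of efficacy parameters: Primary and secondary endpoints" but lists no endpoint. It repeats the aim and extends it only at the end: "a history of late abortion on the perinatal outcome".
- **Section 7.1** has a table of ten outcomes with their tests. None is the outcome of 4.1.1 and none is marked as primary. The nearest rows are "Birth before 34 Weeks of Gestation" and "Fetal / Neonatal Death".
- **Section 7.2** sizes the trial on a proportion of 0.80 in the control group and 0.924 in the treatment group, with a pooled two-sided Z-test at 5%, 121 women per group and 80% power. It does not say what the proportion is of.

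Both of the nearest rows in 7.1 are secondary outcomes in section 4.1.2: "Preterm birth before 34 weeks: rate of delivery before 33+6 weeks" and "Fetal or neonatal death: rate of intrauterine demise or neonatal death during the first 24 hours".

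Section 4.2 describes the study as an "Open Multicentre Randomized Controlled Trial".

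**The concern.** A primary outcome has to be definite enough for two analysts to code the same woman in the same way. Here they could differ on when survival is assessed, on whether a fetal loss is a failure, and on whether the outcome is survival alone or survival combined with gestational age at birth. In an open trial these choices could be made after the data are seen.

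The sample size is affected too. An 80% power statement means something only for an outcome whose expected rates are the ones used. If the outcome is survival and loss of the child is much rarer than 20%, the trial is far smaller than its main question needs, and the protocol as written would not show it.

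**Working it through.** **1. Reproduce the plan's figure.** Inputs from 7.2: p₁ = 0.924, p₂ = 0.80, two-sided α = 0.05, power 0.80. The difference is d = 0.124 and the mean proportion is 0.862.

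- Null term: √(2 × 0.862 × 0.138) = 0.4878
- Alternative term: √(0.924 × 0.076 + 0.80 × 0.20) = 0.4798
- n = (1.96 × 0.4878 + 0.8416 × 0.4798)² / 0.124² ≈ 120.3, so 121 per group
- Power at 121 = Φ[(0.124 × √121 − 1.96 × 0.4878) / 0.4798] = Φ(0.850) = 80.2%

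The stated 121 per group reproduces exactly. This takes all 121 per group as analysed; the drop-out allowance in 7.2 is a separate matter.

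**2. What the figures imply.** Read as failures, they are 20% versus 7.6%, about 24 versus 9 women (121 × 0.20 = 24.2; 121 × 0.076 = 9.2). The relative reduction is 0.124 / 0.20 = 62%. The test gives the same result for successes or failures, so the arithmetic does not show which outcome was meant. The proportion rises with treatment, so it could be survival of the child, or birth at or after 34 weeks.

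**3. Which rates the protocol supports.** Section 2.1 gives 11.1% to 28% recurrence of preterm delivery (gestational threshold not stated), and 27% birth before 34 weeks in women with a short cervix under expectant management. A 20% failure rate is of that order. The protocol gives no rate of child loss for the women it enrols, so nothing in it supports 20% failures if the outcome is survival.

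**4. What happens if failures are rarer.** Keep 121 per group, the same test and the same 62% relative reduction (treatment rate = 0.38 × control rate). The lower control rates are assumptions for illustration and do not come from the protocol.

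| Control failure rate | Treatment failure rate | Power at 121 per group | Needed per group for 80% |
|---|---|---|---|
| 20% (7.2) | 7.6% | 80% | 121 |
| 12% (assumed) | 4.56% | 56% | 215 |
| 10% (assumed) | 3.8% | 48% | 262 |
| 5% (assumed) | 1.9% | 26% | 543 |
| 3% (assumed) | 1.14% | 17% | 919 |

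Example, 10% row: d = 0.062 and mean proportion 0.069. The null term is √(2 × 0.069 × 0.931) = 0.3584 and the alternative term is √(0.10 × 0.90 + 0.038 × 0.962) = 0.3557. Power = Φ[(0.062 × 11 − 1.96 × 0.3584) / 0.3557] = Φ(−0.058) = 48%.

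**The case against.** The strongest defence is that the sections are thin but compatible. The rows in 7.1 correspond to secondary outcomes, and the sentence below the table concerns only when secondary data will be complete. The table can therefore be read as covering secondary outcomes, with the test for the primary given in 7.2. A proportion that rises from 0.80 to 0.924 fits a survival-type success directly. The visit table in 6.2 also has an empty row for a developmental test at corrected age, a faint trace of later follow-up of the child. The rest could be left to a statistical analysis plan.

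Much of this stands, and it rules out three stronger readings that a reader might infer.

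- *The sections directly contradict each other.* They need not. Section 7.2 names no outcome, so it cannot conflict with 4.1.1, and a table of secondary outcomes would have no row for the primary.
- *The trial was really sized on birth before 34 weeks.* That row comes first in the table, and 20% is of the order of the preterm-birth figures. This is inference only. Those figures span a wide range, and the 27% is for a different population under expectant management, whereas 4.4 gives the controls progesterone. The direction of the proportions fits survival equally well.
- *Either survival or birth before 34 weeks could pass as the planned main result.* Section 4.1.2 labels both birth before 34 weeks and fetal or neonatal death as secondary, so promoting either would be a visible departure. Free choice between two binary outcomes, each tested at 5%, would give 8.3% to 9.8% false positives for assumed correlations of 0.7 to 0. That is a hypothetical and not a property of this protocol.

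The defence does not supply a definition. On the compatible reading, 4.1.1 still has no time point and no rule for fetal loss, 6.1 still names nothing, and 7.2 still does not say what it counts. Naming the primary outcome and the quantity the trial is powered on belongs in the protocol. The copy reviewed lacks the front pages, the flowchart and a figure in 4.1.2, but the text of 4.1.1, 6.1, 7.1 and 7.2 shows no gap at this point.

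**Conclusion.** The point holds as a failure to define the primary outcome and to tie the power to it. As written, the primary outcome cannot be analysed, and the 80% power is arithmetically correct for an outcome nobody can identify. If the primary is survival, the assumed 20% control failure rate has no support in the protocol. Power would then be about 48% at an assumed 10% loss and 26% at an assumed 5%. Those two figures rest on the illustrative rates, on an unchanged 62% relative reduction, and on all 121 women per group being analysed. Which outcome was intended remains open. What can still be chosen after the data are seen is the definition of the main result: the time point, the handling of fetal loss, and survival alone or combined with gestational age. That should be settled before outcome data are examined.

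**What to change.** By amendment, before outcome data are examined:

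- In 4.1.1, name one primary outcome with its definition, time point and a rule for how fetal loss counts.
- In 6.1, name the same outcome.
- In 7.1, add a row for it or mark its row as primary.
- In 4.1.2, remove it from the secondary list if it stands there. If survival is chosen, reconcile its time point with the 24-hour limit on neonatal death.
- In 7.2, state that 0.80 and 0.924 are rates of that outcome and give their basis, or restate the power at 121 per group for the rates expected.

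The choice of outcome is the sponsor's. The cost is amendment wording. The stated power may become less favourable, and a later survival time point would need that follow-up to be scheduled.

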### 4.1.2. Secondary outcomes:

[figure not shown]
- Offspring
  - Time to birth
    - Preterm birth before 37 weeks: rate of delivery before 36+6 weeks
    - Preterm birth before 34 weeks: rate of delivery before 33+6 weeks
    - Preterm birth before 32 weeks: rate of delivery before 31+6 weeks
    - Preterm birth before 30 weeks: rate of delivery before 29+6 weeks—
    - Preterm birth before 28 weeks: rate of delivery before 27+6 weeks—
  - Birth weight: median weight (g) of the newborns at birth
  - Fetal or neonatal death: rate of intrauterine demise or neonatal death during the first 24 hours
  - Neonatal morbidity: rate of major adverse neonatal outcomes before discharge from the hospital
    - Intraventricular Haemorrhage (IVH): grades III-IV
    - Retinopathy of prematurity
    - Respiratory Distress Syndrome (RDS): grades II-IV,
    - Need for ventilation > 72 h
    - Necrotising enterocolitis
    - Proven or suspected sepsis, antibiotics (>5 days)
    - Need (Duration in days) for neonatal special care (NICU)
  - Harm from intervention
- Mother:
  - Maternal death
  - Significant maternal adverse events (rate):
    - Heavy bleeding: bleeding that requires a medical intervention
    - Cervical tear: cervical rupture due to the pessary placement
    - Uterine rupture: rupture of the uterus due to contractions or surgery
  - Physical or psychological intolerance to pessary: discomfort or pain due to the pessary that makes daily life uncomfortable (number of cases)
  - Rupture of membranes before 32 weeks: rate of—rupture of amniotic membranes before 31+6 weeks
  - Infection/inflammation
  - Hospitalisation for threatened preterm labour before 32 weeks: requirement of hospitalisation due to preterm contractions that need medical treatment to try to stop them before 31+6 weeks (rate)

- Mean hospital stay duration: number of days of admittance at the hospital
- Use of tocolytic treatment: Type of tocolytic, days of treatment, dose

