### **6.2. Methods and timing to assess records and analyze the efficacy parameters.**

The pregnant women will be assessed according to usual obstetrical management in a high-risk pregnancy.

	Regular Preventive Exam 12+0-18+0 WoG	Regular Preventive Exam 34+0 WoG	Postnatal evaluation
Study procedure	study inclusion		
Informed consent signature	x		
randomisation	x		
Pessary placement	x (Pessary-Group)		
Pessary/cerclage removal		x	
progesterone	x	x	
physical exams			
Abdominal US	x	x	
Vaginal US			
BV/trichomonad/mycete			
Neonatal examination			x
Ages & Stages test (corrected age)			

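### The offspring-death outcome stops at 24 hours while morbidity runs to discharge, so a death after day 1 is a non-event in the only death row with a stated test

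*Protocol*

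**What the plan says.** Protocol section 4.1.2 lists two neighbouring offspring outcomes with different windows. Death is "Fetal or neonatal death: rate of intrauterine demise or neonatal death during the first 24 hours". Morbidity is "Neonatal morbidity: rate of major adverse neonatal outcomes before discharge from the hospital", and its items include ventilation for more than 72 hours and "Need (Duration in days) for neonatal special care (NICU").

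The test table in section 7.1 has one row for offspring death, "Fetal / Neonatal Death", with a two-sided Z-test. The primary outcome in section 4.1.1 is "Child's birth and survival", with no time point and no row of its own in that table.

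On timing, section 7.1 says that "the complete data set for the secondary endpoints will be available after the last women enrolled in this study has given birth". It plans to run the secondary analyses immediately at that point.

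The five delivery cut-offs in section 4.1.2 are labelled 37, 34, 32, 30 and 28 weeks, but are defined as delivery before 36+6, 33+6, 31+6, 29+6 and 27+6. Membrane rupture and hospitalisation for threatened labour, both labelled 32 weeks, use 31+6. The inclusion criterion in section 4.10.1 writes the 34-week limit as 34+0.

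**The concern.** The trial aims to prevent preterm birth and to judge benefit by perinatal outcome (section 6.1). The death outcome nevertheless closes after one day, while every neonatal complication is followed to discharge. A preterm baby who dies in intensive care on day 5 counts as a survivor in the death comparison. If treatment shifted some deaths from the first day to later, this row would show a benefit that was only delay.

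Two related slips sit in the same outcome list. Morbidity and NICU days counted to discharge cannot be complete on the day of the last birth. And a birth on 33+6 is a birth before 34 weeks, yet it is not before 33+6.

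**Working it through.** **The plan's own figure.** The protocol gives no number for the death outcome. Its only relevant figure is the arm size in section 7.2: 0.80 versus 0.924, two-sided 5%, 80% power, pooled Z-test.

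n = [1.96·√(2·0.862·0.138) + 0.842·√(0.924·0.076 + 0.80·0.20)]² / 0.124² = (0.956 + 0.404)² / 0.01538 ≈ 120.3, so 121 per arm (power 80.2%).

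This reproduces the stated size. It serves below only as the denominator.

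**Where a death after 24 hours and before discharge would count**

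| Place | Window | How the death counts |
|---|---|---|
| 4.1.2 death outcome and its row in 7.1 | in utero or first 24 hours | non-event |
| 4.1.2 morbidity | to discharge | only if a morbidity item is met, and not as a death |
| 4.1.1 primary outcome | none stated | undetermined |
| 6.2 schedule | one undated postnatal column; the "Ages & Stages test (corrected age") row shows no mark or date in the text at hand | supplies no horizon |
| 5.2 and 5.3 safety | adverse event reporting | notification, not a comparison of arms |

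A baby who dies on day 2 or 3 cannot meet the item of ventilation beyond 72 hours. NICU need has no minimum duration and would catch most such babies.

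**Scale.** For each 1% of babies who die between 24 hours and discharge:
- per arm: 0.01 × 121 = 1.21; overall: 0.01 × 242 = 2.42
- if 90% to 100% of them meet a morbidity item (assumption), the number outside both rows is 1.21 × (1 − 0.90) = 0.12 down to 1.21 × (1 − 1.00) = 0 per arm

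**Information lost, illustration only.** Assume a control risk of death to discharge of 5%, 10% or 15%, a relative risk of 0.5 that is the same early and late, and a share s of deaths inside the 24-hour window. Expected events are 121 × control risk × 1.5 × s; power is for the pooled Z-test.

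| Control risk | s = 1 | s = 0.5 | s = 0.25 |
|---|---|---|---|
| 5% | 9.1 events, 17% | 4.5 events, 11% | 2.3 events, 7% |
| 10% | 18.2 events, 31% | 9.1 events, 17% | 4.5 events, 11% |
| 15% | 27.2 events, 45% | 13.6 events, 24% | 6.8 events, 14% |

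Power is low throughout. What is lost is completeness of the death count rather than a test that would otherwise have been adequate.

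**Timing.** Simulation of 18 scenarios with 2000 runs each, all inputs assumed except n = 242 and entry at 12+0 to 18+0 weeks:
- enrolment uniform over 1, 2 or 3 years
- 14% or 20% of births before 34 weeks (uniform over 24 to 34 weeks) and 30% or 40% before 37 weeks; the rest at 37+0 to 41+3
- term stay 3 days; preterm discharge at 36, 38 or 40 weeks postmenstrual age, minimum 3 days

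On the date of the last birth, a mean of 1.24 to 2.20 babies are still in hospital (0.51% to 0.91% of 242), of whom 0.00 to 0.90 are preterm. The count includes the last-born, so the excess is 0.24 to 1.20. The wait to the last discharge averages 3.0 to 8.2 days, with a 95th percentile of 3.0 to 27.4 days.

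**Cut-offs.** Assume 20% of an arm deliver before 34 weeks: 0.20 × 121 = 24.2 births. Spread over the last 16 weeks (112 days), 24.2/112 = 0.22 fall on 33+6; over the last 4 weeks (28 days), 24.2/28 = 0.86.

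**The case against.** The strongest reply is that offspring survival is the primary outcome. A primary without a time point does not exclude later deaths, and the text of section 7.1 speaks of Z-tests and relative risks for the outcomes in general, not only for those in its table. A death on day 5 might therefore be counted as a failure in the primary analysis, leaving the 24-hour row as a narrow early-death secondary. On that view the root defect is the undated primary.

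This stands in part: a later death is not shown to escape every test. But nothing in the protocol says that it is counted, and the proportions in section 7.2 are not tied to a named outcome. Dating the primary would also leave a row headed fetal and neonatal death that omits most of the neonatal period.

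It can also be said that two outcomes may have different windows, and that a 24-hour rule is explicit, reproducible and equal in both arms. That is true, and the rule is not ambiguous. The objection is to what it leaves out, for which the protocol gives no reason.

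The criticism of the numbers is fair. The death and timing figures rest on assumptions, and the 3-day lower end of the wait only returns the assumed term stay. The cut-offs are a notation slip: each line carries its own label, and the tested row in section 7.1 names 34 weeks. Parts of the flowchart and schedule cannot be read in the text at hand, so later follow-up may be planned, but that would not change the written definition of the death outcome.

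**Conclusion.** The concern holds. As written, every death between 24 hours and discharge is a non-event in the only offspring-death row with a stated test, and no other dated outcome reports these babies as deaths. That follows from the wording alone. The number of deaths missed cannot be derived from the protocol; 1.2 per arm for each 1% is a scale, not an estimate.

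The timing statement contradicts the outcomes that run to discharge, but under the assumed recruitment and stay it affects only one or two babies. The cut-off notation contradicts its own labels and probably moves less than one birth per arm at 34 weeks, under a rule equal in both arms. The death window should be corrected; the other two points are minor corrections to make at the same time.

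**What to change.** - Define the secondary outcome as intrauterine death or death before hospital discharge, and report death in the first 24 hours as a descriptive split. A composite of death or morbidity is optional.
- When the primary survival outcome is given a time point, align it with this horizon so that the primary, the secondary and the test table agree.
- Analyse the neonatal outcomes after the last baby has been discharged.
- Write the cut-offs as delivery before 37+0, 34+0, 32+0, 30+0 and 28+0, and membrane rupture and hospitalisation as before 32+0, in the notation that section 4.10.1 already uses.

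The cost is mostly wording. Vital status at discharge must be recorded for each baby, but morbidity already requires follow-up to that point. Under the assumptions above, the analysis moves by about 3 to 8 days on average and rarely by more than four weeks.

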#### 4.10. Selection and withdrawal of subjects

##### **4.10. 1 Inclusion criteria.**

- Women with a singleton pregnancy and a history of at least one previous preterm delivery before 34+0 weeks and/or a history of late abortion
- 12+0 -18+0 weeks of gestation
- Minimal age of 18 years
- Informed consent signature

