## **7.4. Selection of subjects to be included in each analysis.**

The analysis will include all the subjects that have been randomised.

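### Neonatal morbidity leaves out death but is tested per pregnancy among all randomised women, so losses count as free of morbidity and the relative risk is biased against the arm with more survivors

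*Protocol*

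**What the plan says.** Four parts of the protocol bear on this.

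- **Outcome (section 4.1.2).** Neonatal morbidity is given as "Neonatal morbidity: rate of major adverse neonatal outcomes before discharge from the hospital". The list below it has severe intraventricular haemorrhage, retinopathy, respiratory distress syndrome grades II-IV, ventilation beyond 72 hours, necrotising enterocolitis, sepsis or more than 5 days of antibiotics, and need for neonatal special care (with its duration in days). Death is not on the list.
- **Death (sections 4.1.1 and 4.1.2).** Death is a separate secondary outcome: "Fetal or neonatal death: rate of intrauterine demise or neonatal death during the first 24 hours". The primary outcome is "Child's birth and survival", with no time point.
- **Test (section 7.1).** "Two-sided Z-tests will be used for comparing among exposure and outcomes groups per pregnancy". The table gives neonatal morbidity its own row, with a two-sided Z-test, relative risk and confidence interval. Fetal or neonatal death has another row. NICU days have none.
- **Analysis set (section 7.4).** "The analysis will include all the subjects that have been randomised".

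Women enter at "12+0 -18+0 weeks of gestation" (section 4.10.1), before any neonatal outcome can exist. Nothing in the protocol limits the morbidity denominator to live births, or makes death a component, a worst rank or a competing event.

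**The concern.** A pregnancy lost after randomisation stays in the denominator of the morbidity rate but cannot contribute an event. It therefore scores the same as a healthy term baby. A liveborn baby who dies before any listed condition is recorded scores the same way.

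The pessary is meant to prolong pregnancy. One effect it could have is to turn a loss into a live but very preterm birth. That baby is better off than if it had died, yet if it has a listed condition it adds an event to the pessary arm. Conversely, a treatment that caused losses could lower the measured morbidity. The morbidity relative risk can then point away from the net effect on the child, and a reader could take it as a sign of harm or of benefit.

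The separate death row does not fully close the gap, because the two secondary outcomes run over different periods: 24 hours after birth for death, and up to discharge for morbidity.

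**Working it through.** **Plan's own figure.** The protocol states no expected rate for neonatal morbidity or death. Its sample size of 121 per arm reproduces (0.80 vs 0.924, two-sided 5%, pooled Z-test: power 80.2%). It is used here only as the denominator, and it cancels from a relative risk over all randomised women.

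**Assumed inputs (none are in the protocol).** Deaths without a listed morbidity: 10 control, 4 pessary, so 10 - 4 = 6 babies saved. Of these six, k have a listed morbidity (k = 2, 4, 6). Other morbid babies: 12 in control, m in the pessary arm. The case m = 12 means no pessary effect on those other babies. The case m = 8 allows some benefit there too.

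**Formulas (pessary over control).**
- Morbidity alone: [(m + k)/121] / [12/121] = (m + k)/12
- Death or morbidity: [(4 + m + k)/121] / [(10 + 12)/121] = (4 + m + k)/22

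| m | k | Morbidity alone | Death or morbidity |
|---|---|---|---|
| 12 | 2 | 14/12 = 1.17 | 18/22 = 0.82 |
| 12 | 4 | 16/12 = 1.33 | 20/22 = 0.91 |
| 12 | 6 | 18/12 = 1.50 | 22/22 = 1.00 |
| 8 | 2 | 10/12 = 0.83 | 14/22 = 0.64 |
| 8 | 4 | 12/12 = 1.00 | 16/22 = 0.73 |
| 8 | 6 | 14/12 = 1.17 | 18/22 = 0.82 |

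In every row the morbidity-only figure is less favourable to the pessary. The combined relative risk is a weighted average of the death relative risk (4/10 = 0.40, weight 10/22) and the morbidity relative risk (weight 12/22). Leaving death out drops the term in which the surviving arm does better.

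**Wider range.** With m = 12, 2 to 8 deaths averted, and 25% to 100% of the saved babies morbid, morbidity alone runs from 1.04 to 1.67 and death or morbidity from 0.73 to 1.00.

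**Restricting to survivors.** The denominators become 121 - 4 = 117 and 121 - 10 = 111, so each morbidity figure is multiplied by 111/117 = 0.949. For m = 12 this gives 1.11, 1.27 and 1.42; for m = 8 it gives 0.79, 0.95 and 1.11. The shift remains, and the groups are now selected by an outcome that treatment may change.

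**Precision.** With m = 12 and k = 3, morbidity alone is 15/121 vs 12/121, relative risk 1.25 (95% CI 0.61 to 2.56). Death or morbidity is 19/121 vs 22/121, 0.86 (0.49 to 1.51). At this trial size the direction of the estimate is at stake, not a significant result.

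**Gap between the two outcomes.** Take a baby who dies on day 2. It is past the 24-hour limit of the death outcome, and can no longer reach 72 hours of ventilation or 5 days of antibiotics. Unless another listed item was recorded first, neither secondary outcome counts it.

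**The case against.** **The scoring is inferred.** The protocol never says in words how a death is scored for morbidity. In a singleton trial, per pregnancy may only name the unit, and a statistical analysis plan that is not shown may set another denominator. That is fair as to wording. But the protocol itself fixes the content of the outcome, the unit, the test and the analysis set, and followed as written they give this score. A denominator of survivors would not cure it.

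**Many babies who die will still count.** A reader might infer that every fetus or baby that dies scores as free of morbidity. The documents do not support that. Respiratory distress syndrome, haemorrhage or need for special care may be recorded before death, and that baby is then an event. The problem is confined to fetal losses and to early deaths before any listed condition is diagnosed.

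**The reversal can be built in.** Holding the other morbid babies at 12 in both arms assumes no pessary effect on them. With 8 in the pessary arm, only k = 6 gives a figure above 1. With 6, the figures are 8/12 = 0.67, 10/12 = 0.83 and 12/12 = 1.00, with no reversal. This objection stands: reversal is possible, not established.

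**NICU days.** A reader might infer that NICU days are compared per pregnancy across all randomised women. Section 7.1 has no such row, and its row for days of hospitalisation may be maternal, so no such comparison can be attributed to the protocol.

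**Death is visible elsewhere.** Survival is in the primary outcome and death has its own row, so morbidity can be read beside them. This limits the harm but does not remove it, because the morbidity row carries its own relative risk and test, and the death row stops at 24 hours.

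**Conclusion.** The point holds as a possible bias in one secondary outcome. As defined and analysed, neonatal morbidity counts fetal losses and some early deaths as good outcomes, and a death after 24 hours and before discharge can fall outside both secondary outcomes. If survival differs between arms, the morbidity relative risk is biased against the arm with more survivors as a measure of net effect on the child.

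On the assumed counts it is 1.17 to 1.50 where death or morbidity gives 0.82 to 1.00, or 0.83 to 1.17 where death or morbidity gives 0.64 to 0.82. The size rests wholly on those assumptions. If the pessary does not change survival, this differential bias does not arise.

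A reader might go further and conclude that an effective pessary will look harmful, or that losses will be frequent because many participants have had a late abortion. Neither is supported: the first depends on the assumed counts, and the protocol gives no proportion for the second. The primary outcome includes survival and is not affected.

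**What to change.** In section 4.1.2 and in the neonatal morbidity row of section 7.1, make the compared outcome: fetal or neonatal death, or major neonatal morbidity, before discharge, counted once per randomised pregnancy. Show death and each morbidity separately beside it, with death followed to discharge and not only to 24 hours. Take NICU duration out of the rate; if it is compared, do so by ranks with death ranked worst.

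The cost is one definition, one table row, and recording deaths to discharge, which is the follow-up already used for morbidity. The downside is that the composite mixes death with less serious events, so it must not be reported without its components.
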